The secondary outcome response variables are time to hospital discharge, and measures of parasite clearance calculated from parasite density, as measured by thick blood smear such as parasite clearance half-life, total parasite clearance by Day 2, and time to 90% reduction in parasitemia. Parasite clearance half-life (PCT₅₀) and time to 90% reduction (PCT₉₀) will be estimated using the WorldWide Antimalarial Resistance Network (WWARN) parasite clearance estimator (PCE) algorithm (Flegg 2011). The relationship between AUC_{0-12} and C_{max} and the time-to-event response variables will be analyzed using Cox proportional hazards regression.

The relationship between AUC_{0-12} and C_{max} and the binary variable of total parasite clearance by Day 2 will be analyzed using logistic regression. Covariates will include exposure and potential confounding variables. The full list of covariates to be considered and the variable selection strategy will be described in the SAP. Analyses of secondary outcome variables will not be adjusted for multiplicity.

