2.1. Purpose of the Analyses

This is a phase 4 open-label study to assess the PK and PD of the standard of care IV artesunate in Ugandan children 6 months-14 years of age diagnosed with severe malaria. The study is intended to inform dosing regimens of IV artesunate by evaluating the relationships between DHA exposures after IV artesunate and markers of physiologic dysfunction associated with severe malaria. This study will also secondarily and exploratorily assess the relationships between *P. falciparum* parasitemia and DHA exposures for comparison with historical studies and between DHA exposures and other clinically relevant measures of successful treatment, including time to hospital discharge and neurodevelopmental outcomes associated with severe malaria.

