8.2.2. Parasite Clearance

We will additionally perform secondary analyses to assess the relationship between measures of DHA exposure, again including AUC_{0-12} , C_{\max} , $t_{1/2}$ and T_{\max} , and measures of parasitemia clearance. The outcome response variables for these analyses are measures of parasite clearance calculated from parasite density, as measured by thick blood smear, including parasite clearance half-life (PCT_{50}), total parasite clearance by Day 2, and time to 90% reduction in parasitemia (PCT_{90}).

PCT_{50} and PCT_{90} will be estimated using the WWARN PCE algorithm [\[4\]](#). PCT_{50} is the time from first on-study dose needed for parasitemia to be reduced by half during the log-linear phase of parasite clearance, and can be calculated by $PCT_{50} = \log_e(2)/K$, where K is the first-order clearance rate constant. PCT_{90} is the time from first on-study dose needed for parasitemia to be reduced by 90% during the log-linear phase of parasite clearance, and can be calculated by $PCT_{90} = \log_e(10)/K$. The first-order clearance rate constant K is typically equal to the negative slope of the log-parasitemia-time linear relationship during the log-linear phase of parasite clearance.

PCT₅₀ and PCT₉₀ will be estimated using the parasite density per μL . The parasite density per μL will be calculated using the formula: Number of parasites per 200 WBCs \times 40 = asexual parasites / μL . The clearance rate constant K will be calculated using the following steps according to the WWARN PCE algorithm [4] for each participant separately.

1. Perform data cleaning. Data cleaning will proceed in order as follows:
 - a. Removal of data from recurrences of parasitemia including any measurements after 7 days, measurements after a time when 2 measurements are >24 h apart, and data after the last measured zero parasitemia if the positive measurements before and after this measurement are separated by >24 h are removed.
 - b. Removal of all trailing zeros after the last nonzero parasitemia except the first zero.
 - c. Removal of repeated parasitemia measurements $<100/\mu\text{L}$ and data that fall between them.
 - d. Replacement of the first zero parasitemia measurement directly after the last positive parasitemia with the limit of detection ($40/\mu\text{L}$ [4]).
 - e. Removal of extreme values outside of the range ($0, 3 \times 10^6$) or measurements with times below zero.

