**Step 5: END**

6. End.

PCT_{50} and PCT_{90} for each participant will then be estimated using the formulas described previously in this section. Individual estimates of K and t_{lag} will be presented in [Listing 15](#). The following pseudocode will be used to fit cubic normal and tobit regression models and to calculate model-predicted values for each participant's log-parasite density data.

```

/* Cubic Regression with Predicted Values by Participant ID */
data clearance; set clearance;
time2=time**2; time3=time**3;
log_density=log(density);
run;
proc reg data=clearance;
model log_density=time time2 time3 / p;
  
```

```

by partid;
ods output OutputStatistics=predicted;
run;

/* Cubic Tobit Regression with Predicted Values by Participant ID */
data clearance; set clearance;
time2=time**2; time3=time**3;
log_density=log(density);
/*replace parasite density values = the lower limit for the variable with.*/
if density=LOD then lower=.;
else lower=log_density;
run;
proc lifereg data=clearance outest=OUTEST(keep=partid _scale_);
  model (lower, log_density) = time time2 time3 / d=normal;
  by partid;
  /*output mean of uncensored variable*/
  output out=OUT xbeta=Xbeta;
run;
data predict; merge out outest; by partid;
  lambda = pdf('NORMAL',Xbeta/_scale_);
  / cdf('NORMAL',Xbeta/_scale_);
  /*calculate mean of censored variable*/
  predict = cdf('NORMAL', Xbeta/_scale_)
    * (Xbeta + _scale_*lambda);
run;

```

Total parasite clearance by Day 2 will be a binary variable indicating whether total parasite clearance has occurred within the first 50 hours post-first dose of IV artesunate. Total parasite clearance will be determined using all thick blood smears collected within the 50 hours from the first dose of IV artesunate. Total parasite clearance by Day 2 will be determined for participants in the PD Analysis Population with any results of thick blood smears available within 50 hours after the first dose of IV artesunate.

The relationship between AUC_{0-12} , C_{max} , $t_{1/2}$ and T_{max} , and the time-to-event response variables of PCT_{50} and PCT_{90} will be analyzed using Cox proportional hazards regression. One Cox proportional hazards regression model will be fit for each response variable and DHA exposure parameter. Covariates in these models will include the appropriate exposure parameter as well as a subset of the covariates given in Section 6.4.

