Planned Timepoint ^a	PD Analysis Population (N=X)			PD Analysis Population, No Prior IV Artesunate or Other Artemisinin-Based Therapy Subset (N=X)		
	N*	n	%	N*	n	%
0 (0-2) h	x	x	xx	x	x	xx
6 (4-8) h	x	x	xx	x	x	xx
12 (10-14) h	x	x	xx	x	x	xx
24 (22-26) h	x	x	xx	x	x	xx
36 (34-38) h	x	x	xx	x	x	xx
48 (46-50) h	x	x	xx	x	x	xx
Day 3	x	x	xx	x	x	xx
Day 4	x	x	xx	x	x	xx
Day 5	x	x	xx	x	x	xx

Notes: N = Number of participants in the analysis population or subset. N* = Number of participants in the analysis population or subset with parasitemia results available at the respective timepoint.
 Proportion (%) cleared is calculated using N* as the denominator.
^a Timepoints are given post-first on-study dose of IV artesunate.

Table 25: Assessment of Relationships between Time to Percent Reduction of Parasitemia and Exposure Parameters by Parasite Clearance Parameter, Exposure Parameter, and Analysis Population

Analysis Population	Parameter	PK Exposure Parameter												
		AUC ₀₋₁₂ (ng*h/mL)				C _{max} (ng/mL)			T _{max} (h)			t _{1/2} (h)		
		N*	Hazard Ratio ^a	95% CI	N*	Hazard Ratio ^a	95% CI	N*	Hazard Ratio ^a	95% CI	N*	Hazard Ratio ^a	95% CI	
PD Analysis Population (N=X)	PCT ₅₀ (hours)	x	xx.x	(xx.x, xx.x)	x	xx.x	(xx.x, xx.x)	x	xx.x	(xx.x, xx.x)	x	xx.x	(xx.x, xx.x)	
	PCT ₉₀ (hours)	x	xx.x	(xx.x, xx.x)	x	xx.x	(xx.x, xx.x)	x	xx.x	(xx.x, xx.x)	x	xx.x	(xx.x, xx.x)	
PD Analysis Population, No Prior IV Artesunate or Other Artemisinin-Based Therapy Subset (N=X)	PCT ₅₀ (hours)	x	xx.x	(xx.x, xx.x)	x	xx.x	(xx.x, xx.x)	x	xx.x	(xx.x, xx.x)	x	xx.x	(xx.x, xx.x)	
	PCT ₉₀ (hours)	x	xx.x	(xx.x, xx.x)	x	xx.x	(xx.x, xx.x)	x	xx.x	(xx.x, xx.x)	x	xx.x	(xx.x, xx.x)	
Notes: N = Number of participants in each analysis population or subset. N* = Number of participants in each analysis population or subset with estimable PK parameter and for which the parasite clearance and PK exposure parameters can be calculated. CI = Confidence interval. PCT ₅₀ = Half-life of parasite clearance from time of first on-study IV artesunate dose. PCT ₉₀ = Time to 90% reduction in parasitemia from first on-study IV artesunate dose.														
^a Hazard ratios and 95% CIs are estimated using a Cox proportional hazard model adjusted for the PK exposure parameter and other covariates. See Table 26 for covariates included in each analysis model.														

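### PCT50 and PCT90 are rescaled fitted slopes analysed only by Cox regression, so no planned result gives the size of a change in half-life, and the two endpoints duplicate each other

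*SAP*

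**What the plan says.** SAP 8.2.2 computes PCT50 as ln(2)/K, "where K is the first-order clearance rate constant", and PCT90 as ln(10)/K, described as the time "needed for parasitemia to be reduced by 90% during the log-linear phase of parasite clearance". K itself "is typically equal to the negative slope of the log-parasitemia-time linear relationship during the log-linear phase of parasite clearance", and is estimated child by child with the WWARN algorithm.

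For inference, Protocol 11.3.5 states that "the time-to-event response variables will be analyzed using Cox proportional hazards regression". SAP 8.2.2 applies this to both variables: "One Cox proportional hazards regression model will be fit for each response variable and DHA exposure parameter". Results are hazard ratios per one-unit change in exposure (Table 25, Figures 216 and 217).

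The only Cox code, and the only censoring rule (SAP 6.2), are for hospital discharge. Children in whom K cannot be estimated do not enter the models: the analysed number in Table 25 is restricted to those "for which the parasite clearance and PK exposure parameters can be calculated". The note to Table 26 makes actual time of collection a minimum covariate in every PCT50 and PCT90 model.

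Descriptively, the SAP plans boxplots of both variables by covariate (Figures 212 and 213) and a listing of K and lag time (Listing 15). Time to discharge has a table of mean, SD, median and range (Table 20). PCT50 and PCT90 have none.

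**The concern.** A half-life computed from a slope is a continuous measurement, fully known once K is known. Nothing happens to the child at that time, nobody leaves a risk set, and nobody is censored. Calling it a time-to-event variable appears to carry the discharge template over to a different kind of outcome. The required collection-time covariate points the same way, since a slope fitted to several smears has no single collection time.

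At stake is what a reader can learn about a secondary objective, the relation between DHA exposure and parasite clearance. SAP 2.1 places this work on parasitemia and "DHA exposures for comparison with historical studies". The planned inference gives the direction and strength of association. It does not say by what percentage, or by how many hours, half-life changes with exposure. Table 25 would also show two rows of results per population that look like two pieces of evidence.

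**Working it through.** The plan states no effect size, power or distribution for PCT50 or PCT90, so there is no planned figure to reproduce. The checks use the SAP's formulas plus assumptions labelled as such.

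**1. Relation between the endpoints.** PCT90/PCT50 = [ln(10)/K] / [ln(2)/K] = ln(10)/ln(2) = 2.3026/0.6931 = 3.322. K cancels, so the ratio is the same in every child. The lag time is estimated but enters neither formula, although both quantities are described as counted from the first on-study dose.

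**2. What Cox uses.** The partial likelihood depends on the outcome only through its ordering. Multiplying every value by 3.322 leaves each risk set unchanged, as does any other increasing transformation. This was checked on simulated data. Assumptions: ln K = ln(0.25) + 0.1 × exposure in SD units + normal error with SD 0.3; sex as a covariate; every child counted as an event; Breslow ties.

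| N | HR, PCT50 | HR, PCT90 | HR, PCT50 cubed | Geometric mean ratio, linear model (same for PCT50 and PCT90) |
|---|---|---|---|---|
| 46 | 1.768 | 1.768 | 1.768 | 0.854 |
| 75 | 1.376 | 1.376 | 1.376 | 0.878 |
| 100 | 1.458 | 1.458 | 1.458 | 0.902 |

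Standard errors for PCT50 and PCT90 were also identical. Cubing turns a 10% shortening (ratio 0.9) into a 27% shortening (0.9³ = 0.729), and the hazard ratio does not move. The true ratio of half-lives in this simulation is exp(−0.1) = 0.905 per SD. The last column estimates that ratio directly.

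**3. One effect, many hazard ratios.** Fix the effect at a 10% shorter half-life per SD of exposure. Under a Weibull model with scale s, HR = exp(−ln(0.9)/s) = exp(0.1054/s). The lognormal column was simulated with residual SD s.

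| s (assumed) | HR, Weibull | HR, lognormal (approx.) |
|---|---|---|
| 0.2 | 1.69 | 1.63 |
| 0.3 | 1.42 | 1.42 |
| 0.4 | 1.30 | 1.29 |
| 0.6 | 1.19 | 1.15 |

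**4. The reverse reading.** Take a reported HR of 1.42 (ln = 0.351). Under the Weibull model the half-life ratio is exp(−0.351 × s). At s = 0.2 it is exp(−0.070) = 0.93, a 7% shortening. At s = 0.6 it is exp(−0.211) = 0.81, a 19% shortening. The hazard ratio alone cannot separate these.

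**5. Number of distinct analyses.** Table 25 implies 2 parameters × 4 exposure parameters × 2 populations = 16 fits. With the same covariates and no rounding, only 8 are distinct.

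**The case against.** Cox regression does not need censoring. On fully observed positive values it is a legitimate rank-based analysis. In simulations under normal and extreme-value errors, both Cox and the log-scale linear model held about 5% type I error (0.046 to 0.060). The objective is to determine a relationship, and a hazard ratio with its interval addresses that. The protocol prespecifies Cox, and the endpoint is secondary, unadjusted for multiplicity, in a study described as hypothesis-generating. All of this stands, and it is why Cox should stay.

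A reader might infer that half-life is never summarised. The documents do not support that: Figures 212 and 213 show both variables, and each half-life can be rebuilt from Listing 15 as ln(2)/K.

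A reader might also infer that the comparison with historical studies is impossible. That is not shown either. The purpose is stated for parasitemia in general, and Tables 23, 24 and 27 give density, proportion cleared and odds ratios for clearance by Day 2. The documents do not say which effect measure the historical studies reported.

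A third tempting reading is that the linear model is more powerful. With normal log half-lives, Cox has relative efficiency 0.82. With an extreme-value shape the order reverses (simulated power 0.96 for Cox against 0.88 for linear at N=75, R² 0.12). The documents give no distribution, so no claim about power follows. An argument from non-proportional hazards depends on the same unknown.

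Finally, leaving out children without K is not a fault of Cox, because a linear model leaves out the same children.

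**Conclusion.** The point holds as one of interpretability and duplication, not of validity. Three parts follow from the SAP's own definitions without any distributional assumption: PCT50 and PCT90 are rescaled slopes with no event or censoring rule; the Cox hazard ratio carries no half-life scale; and the PCT50 and PCT90 fits coincide when covariates are the same and values are unrounded. If different covariates were chosen for the two, their results would differ only for that reason.

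The size of the ambiguity rests on assumed residual spreads. Over a scale of 0.2 to 0.6, a fixed 10% effect gives Weibull hazard ratios from 1.69 to 1.19. The documents also do not state how many children will have an estimable K. This is a cheap improvement to a secondary analysis. It leaves the primary analysis untouched.

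**What to change.** - In SAP 8.2.2 and Tables 25 and 26, add a linear regression of ln(PCT50) on each exposure parameter with the same baseline covariates. Report the geometric mean ratio as a percentage change in half-life with 95% CI. Keep the protocol's Cox model alongside.
- Remove actual time of collection as a required covariate for these models in Table 26.
- Report the PCT50/PCT90 result once, or define PCT90 as a time from dose that includes the lag, so that it becomes a separate quantity.
- Add a table in the style of Table 20 for PCT50 in both populations: number estimable, number not estimable with reason, geometric mean, median and range.
- Record the change in SAP Section 15, which already lists departures from Protocol 11.3.5. Protocol 11.3 gives the SAP precedence where the two differ.

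The cost is SAP wording, one simple model and one table, all on data already derived. The linear model relies on roughly normal log half-lives, to be checked with residual plots. Children without an estimable K remain excluded under either model, and the new table would show how many there are and why.

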8.3. Exploratory Pharmacodynamics Analyses

Details of planned analyses for exploratory PD outcome measures will be provided in an addendum to this SAP.

9. SAFETY EVALUATION

9.1. Demographic and Other Baseline Characteristics

Sex, ethnicity, race, and town/village of residence will be summarized for all participants in the Safety Population ([Table 10](#)). Ethnicity will be categorized “Hispanic or Latino,” or “Not Hispanic or Latino,” “Unknown,” or “Not Reported.” In accordance with National Institutes of Health (NIH) reporting policies, participants may self-designate as belonging to more than one race or may refuse to identify a race.

Weight-for-age and height-for-age z-scores will be determined for participants younger than 60 months based on WHO Child Growth Standards [\[2\]](#). Age at enrollment, weight, height, weight-for-age z-score, and height-for-age z-score will be summarized by sex ([Table 11](#)).

Individual participant listings will be presented for all demographic and baseline characteristics ([Listing 6](#)).

9.1.1. Prior and Concurrent Medical Conditions

Number and percentage of participants’ pre-existing and concurrent medical conditions will be summarized by MedDRA® System Organ Class (SOC) for the Safety Population ([Table 12](#)).

Individual participant listings will be presented for all pre-existing and concurrent medical conditions ([Listing 7](#)).

9.1.2. Prior and Concomitant Medications

Concomitant medications include any traditional, herbal, supplement, and over-the-counter medicine administered during the period starting from 7 days before enrollment and ending at the end of the study follow-up period.

All concomitant medications will be coded to the Anatomical Therapeutic Classification (ATC) using the current WHO Drug Dictionary. The use of concomitant medications taken during the study will be summarized by ATC 1 and ATC 2 in [Table 45](#). If a participant took a specific medication multiple times or took multiple medications within a specific therapeutic class, that participant would be counted only once for the coded drug name or therapeutic class. Individual participant listings will be presented for all concomitant medications ([Listing 22](#)).

9.2. Measurements of Treatment Compliance

Participants may have received IV artesunate before enrollment in the study. The number of participants who received IV artesunate before enrollment will be given in [Table 5](#).

Date and time of IV artesunate administrations including any administered before enrollment will be included in [Listing 8](#). Date and time of oral ACT administration will be included with the name of treatment received in [Listing 9](#).

The number and proportion of enrolled participants receiving IV artesunate and oral ACT will be summarized by dose and timing of dosing (pre-enrollment or on-study) in [Table 8](#). Overall individual compliance data for IV artesunate administered before enrollment and on-study and oral ACT will be presented, including the treatments and numbers of doses received and whether participants were able to transition to oral antimalarial therapy per guidelines with the reason if not ([Listing 10](#)).

9.3. Adverse Events

An overall summary of adverse events for participants in the Safety Population will be presented in [Table 29](#). This summary will include the numbers of participants with at least one AE, at least one related AE, at least one SAE, at least one AE leading to early termination.

9.3.1. Solicited Events and Symptoms

There are no solicited events or symptoms collected for this study.

9.3.2. Unsolicited Adverse Events

A listing of all unsolicited AEs will be presented ([Listing 16](#)) with information regarding onset, duration, severity, relationship to study product or study procedures, and outcome. A participant listing of non-serious AEs of moderate or greater severity will also be reported in [Table 32](#).

The number and proportion of participants experiencing unsolicited AEs will be summarized by MedDRA SOC and PT, severity, and relationship to study product or study procedures in [Table 30](#). The percentage of participants reporting unsolicited AEs related to IV artesunate, related to oral ACT, and related to study procedures will be summarized graphically by MedDRA SOC and maximum severity in [Figure 220](#). The number of related AEs reported will be presented graphically by whether related to IV artesunate, oral ACT, or study procedures, as well as by MedDRA SOC and maximum severity in [Figure 219](#).

9.4. Deaths, Serious Adverse Events and other Significant Adverse Events

Individual data listings of deaths and other SAEs will be provided ([Table 31](#)). The listing will include participant ID, AE description, onset, duration, MedDRA SOC and PT, reason reported as an SAE, severity, relationship to study treatment or procedures, alternate etiology if not related, action taken with study treatment, whether the participant discontinued due to the AE, and AE outcome.

9.5. Pregnancies

This is a study of IV artesunate in Ugandan children 6 months-14 years of age diagnosed with severe malaria according to standardized WHO criteria. Given the age range of the study population, pregnancies are not expected to occur, and pregnancy information was not collected.

9.6. Clinical Laboratory Evaluations

Biochemistry laboratory evaluations, hematology laboratory evaluations, and dipstick urinalysis will be performed at Screening and on Day 1, Day 2, Day 3, Day 4, Day 5, Day 6, and Day 7 (± 2), with serum bicarbonate additionally assessed on Day 14 (± 2) and hemoglobin additionally assessed on Day 14 (± 2) and Day 28 (± 4). Hematology laboratory evaluations will also be performed at the final study visit on Day 183 (± 14). Baseline for laboratory evaluations will be defined as given in [Section 3.3](#).

For tables, listings, and figures, the sort order for biochemistry parameters will be: alanine aminotransferase (ALT), aspartate aminotransferase (AST), blood urea nitrogen (BUN), calcium, creatinine, direct bilirubin, glucose, potassium, serum bicarbonate, serum lactate, sodium, and total bilirubin. The sort order for hematology parameters will be: hemoglobin, neutrophil count, neutrophil %, platelets, and white blood cell count (WBC). The sort order for urinalysis parameters will be: hemolyzed and non-hemolyzed blood, bilirubin, ketones, leukocyte esterase, nitrites, pH, urine glucose, urine protein and urobilinogen.

Abnormalities in clinical laboratories after the baseline visit will be captured as AEs on the appropriate data collection form and eCRF. Abnormalities that are present at baseline will only be reported as AEs after the baseline visit if they have worsened (increased in severity/grade).

All biochemistry results will be presented in [Listing 17](#), all hematology laboratory results will be presented in [Listing 18](#), and all urinalysis results will be presented in [Listing 19](#). Abnormal laboratory results will be recorded as unsolicited AEs in [Listing 16](#).

Summary statistics of measurements and their change from baseline will be presented by continuous laboratory parameter and timepoint for biochemistry ([Table 33](#)) and hematology ([Table 34](#)) parameters. Boxplots of change from baseline at scheduled collection days will be presented by weight group, sex, and timepoint for continuous chemistry parameters beginning at [Figure 221](#) and continuing through [Figure 232](#), and for continuous hematology parameters beginning at [Figure 233](#) and continuing through [Figure 237](#). Urinalysis results will be summarized by scheduled timepoint and parameter beginning in [Table 35](#) and continuing through [Table 43](#).

